### **Analytical Plan**

Results will be analyzed initially using a paired T Test for continuous variables and a Wilcoxon signed-rank test for ordinal variables.

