### **Methods and Measures**

A prospective, randomized, double blind, placebo-controlled AB/BA crossover study is planned in patients electively scheduled to undergo electroconvulsive therapy to treat their medication refractory mood disorders. We aim to have 200 evaluable treatments involving the consent of an estimated 100 subjects. As patients normally require more than 1 electroconvulsive therapy to treat their condition, the patient's consent will allow them to participate in this research study in each of two treatments.

Patients will undergo induction of general anesthesia with methohexitol 1 mg/kg and succinylcholine 1 mg/kg in a standardized anesthetic protocol that is nearly identical to the usual institutional standard of care for electroconvulsive therapy. A copy of the anesthetic protocol is posted for the providers reference at the point of care. Members of the study team will be responsible for randomization of the patients and preparation of the blinded study medication. Randomization to either placebo first then alfentanil or the converse will be carried out on the morning of the first study treatment and allocation concealed within a computerized randomization and data collection instrument (REDCap). Calculation of the study dose is done per the FDA package insert using an automated system within REDCap. Alfentanil (20 mcg/kg) diluted with normal saline to 10cc or placebo, consisting of 10 cc normal saline will be obtained from the OR pharmacy and placed in an identical 10 cc syringe labeled with the patient's name and "Study Drug". Any unused quantity of alfentanil will be wasted per hospital policy in the OR pharmacy. The study drug will be administered by the blinded anesthesia provider caring for the patient per the anesthetic protocol. Data will be collected by members of the study team who are blinded to the randomization. Data will be collected and secured in REDCap stored on the institution's secure internal servers.

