### **Exclusion Criteria**

Under the age of 18

Allergy to alfentanil

Allergy to other standard anesthetic medications utilized in the course of ECT (glycopyrrolate, methohexitol, and succinylcholine)

History of malignant hyperthermia

History of severe airway obstruction, bronchospasm or laryngospasm

History of recent myocardial infarction, ventricular arrhythmia (within six weeks)

Adverse reaction to ECT requiring premedication with lidocaine or atropine

Non-English speaking

Patients unable to consent for themselves

Current pregnancy

Patients who have not yet received four treatments

Anesthesiologist uncomfortable with administering the study drug to the patient

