## **Interventions and Interactions**

Informed consent will be obtained during the assessment with the psychiatrist involved in their care. The patient will be randomized into 2 groups: use of alfentanil with the first treatment or placebo with the first treatment and subsequently cross over to the other therapy for the second treatment. Study medication will be prepared by a member of the study team and the patient as well as all members performing anesthesia and data collection will be blinded to group allocation. All medications utilized in the conduct of this study are the standard anesthetic medications used on a daily basis (with the exception of the alfentanil) during the course of any patient having the ECT procedure and not enrolled in a research study.

A standardized anesthetic regimen will be utilized for each subject and includes the following:

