### **60 SECONDS AFTER STUDY DRUG ADMINISTRATION**

ECT stimulus applied

During the procedure in the operating room, blood pressure and heart rate will be monitored as per standard of care (blood pressure every 1 minute and continuous electrocardiogram, pulse oximetry, and capnography while in the procedure room) until the patient is spontaneously ventilating adequately per anesthesia discretion. Hypertension will be treated if the systolic blood pressure exceeds 185 mmHg using nitroglycerin 400 mcg/mL per usual institutional practice. The full range of usual antiarrhythmic, vasopressor and antihypertensive medications including lidocaine, esmolol, phenylephrine, epinephrine, atropine and ephedrine will be available for use by the anesthesia team should they be required. Use of these medications will be tracked and recorded by the study team. After restoration of adequate spontaneous ventilation the patient will then be moved to recovery for subsequent discharge. Evaluation will be done by study personnel to assess the presence of headache or other potential adverse events prior to discharge, and patient satisfaction with the anesthetic.

Prior to discharge the subjects will be asked to rate the severity of headache (if present) as well as the satisfaction with the anesthetic received. Both will be rated on a scale of 0=no headache as all up to 10=worst headache ever, as well as 0=not satisfied with anesthetic at all up to 10=most definitely satisfied with the anesthetic received.

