### **Outcome Measure(s)**

The primary outcome will be the within-individual absolute difference in systolic blood pressure from baseline to the first blood pressure after the ECT stimulus.

Secondary outcomes include the within-individual differences of heart rate at 15 and 30 seconds post stimulus, absolute difference in diastolic blood pressure from baseline to the first blood pressure after the ECT stimulus, maximum and minimum heart rates, unit doses of nitroglycerin, esmolol, phenylephrine, ephedrine, EEG and motor seizure duration, use of lidocaine, atropine or epinephrine, total in-room time, time to return of spontaneous ventilation after induction, severity of headache in the post anesthesia care unit, and satisfaction with the anesthetic post-procedure.

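### The crossover is randomised by sequence, but the planned paired tests carry no period term: they stay valid, yet any period effect is counted as error and costs precision.

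*Combined protocol and SAP*

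**What the plan says.** Under Methods and Measures: "A prospective, randomized, double blind, placebo-controlled AB/BA crossover study is planned". The same section puts the randomisation at the level of treatment order: "Randomization to either placebo first then alfentanil or the converse will be carried out on the morning of the first study treatment". Interventions and Interactions repeats this: "The patient will be randomized into 2 groups: use of alfentanil with the first treatment or placebo with the first treatment", after which patients "subsequently cross over to the other therapy for the second treatment". The target is 200 evaluable treatments from an estimated 100 subjects.

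The primary outcome (Outcome Measure(s)) is a within-individual "difference in systolic blood pressure from baseline to the first blood pressure after the ECT stimulus". It is continuous, so it falls under the paired t-test.

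The Analytical Plan reads in full: "Results will be analyzed initially using a paired T Test for continuous variables and a Wilcoxon signed-rank test for ordinal variables". No period or sequence term appears anywhere in the document. The word for a first step implies a later analysis, but none is named. Allocation ratio and blocking are not stated.

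**The concern.** Randomising order in a two-period crossover allows a general shift between the first and second occasion to be separated from the treatment effect. A paired t-test or signed-rank test on alfentanil minus placebo ignores which occasion each measurement came from. Any such shift is therefore left in the data as noise.

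Two things are at stake. The first is precision: standard errors and confidence intervals can be wider than the design requires. The second is the estimate in the trial as it turns out: if one sequence has more completers than the other, the period shift does not cancel.

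There is also a prespecification issue. If a period term is added once the data are in, it becomes a choice made with knowledge of the results, and the open wording of the Analytical Plan leaves room for that.

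**Working it through.** **Inputs.** From the documents: 200 treatments / 2 per subject = 100 within-patient differences. The documents give no alpha, target effect, SD or power, so there is no sample-size figure to reproduce. Assumed: two-sided 5% level, SD of within-patient differences 20 mmHg, period effect π from 0 to 15 mmHg. The effect of 5.66 mmHg is the one with 80% power at π = 0 (noncentral t, N = 100).

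**Algebra.** Let D be alfentanil minus placebo, τ the treatment effect and π the second-minus-first period shift.

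- Alfentanil first: mean of D = τ − π. Placebo first: mean of D = τ + π.
- Pooled variance of D, with share q in one sequence: SD² + 4q(1 − q)π². At q = 0.5 this is SD² + π².
- Expected pooled mean: τ + π(n₂ − n₁)/N, where n₂ is the number with placebo first and n₁ the number with alfentanil first.
- Period-adjusted estimate: the average of the two sequence means, with the pooled within-sequence SD on 98 df. π cancels from both the estimate and its standard error.

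**Inflation of the reported standard error at 50/50**, √(1 + π²/400), and the sample size that would give the same reported precision, 100/(1 + π²/400):

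- π = 2: 1.005; 99
- π = 5: 1.031; 94
- π = 10: 1.118; 80
- π = 15: 1.250; 64

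**Simulation** (at least 20,000 trials per cell, effect 5.66 mmHg):

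| π (mmHg) | Paired t power, simple randomisation | Paired t power, exact 50/50 | Adjusted power | Mean 95% CI width, paired v adjusted (simple) |
|---|---|---|---|---|
| 0 | 0.80 | 0.80 | 0.80 | 7.9 v 8.0 |
| 2 | 0.80 | 0.80 | 0.80 | 8.0 v 8.0 |
| 5 | 0.77–0.78 | 0.78 | 0.80 | 8.2 v 8.0 |
| 10 | 0.71 | 0.73 | 0.80 | 8.9 v 8.0 |
| 15 | 0.61 | 0.64 | 0.80 | 9.9 v 8.0 |

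**Validity.** Under simple randomisation the paired t-test rejects a true null in 4.8–5.1% of trials at every π, and the estimate is unbiased on average. With exact 50/50 sequences it becomes conservative: null rejection is about 4.3%, 2.9% and 1.4% at π = 5, 10 and 15. In that case the paired and adjusted point estimates are identical and the true standard error stays at 20/√100 = 2.0. What is lost is that the reported standard error is too large.

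**Unequal sequences.** At 60/40 the shift is π × 20/100 = 0.4, 1.0, 2.0 and 3.0 mmHg at π = 2, 5, 10 and 15. Null rejection, given that split, is about 5%, 7%, 12% and 17%, against about 5% adjusted. Under simple 1:1 randomisation of 100 patients the exact binomial chance of a split of 60/40 or worse is 5.7%. These figures are already averaged into the overall 5%.

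**Ordinal outcomes** (illustration: 0–10 score, mean 4, subject SD 1.2, residual SD 1.5, effect 0.6 points). Signed-rank v rank-sum power: 0.77 v 0.76 at π = 0, 0.75 v 0.77 at π = 0.5, and 0.68 v 0.75 at π = 1.

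**The case against.** The best defence is that the planned test is valid and that a large period effect is unlikely. Patients enter late in their course (the exclusion list includes "Patients who have not yet received four treatments"), the anaesthetic is standardised, and the primary outcome is already net of each session's baseline. Up to π = 5 mmHg, a quarter of the assumed SD, the loss is at most about 3 power points. That stands, and it limits the weight of the point. It does not close it. Subtracting baseline removes a shift in baseline pressure but not a shift in the response to the stimulus. The interval between the two study treatments is not fixed, and on the stimulus the protocol says only "ECT stimulus applied". Unfixed settings do not by themselves produce a common shift, but nothing in the documents rules one out.

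It can also be said that a 5.66 mmHg effect sits on the steep part of the power curve. That is fair. At a true effect of 10 mmHg the paired t-test has power 0.999, 0.998, 0.993 and about 0.98 at π = 0, 5, 10 and 15, and at 15 mmHg both tests have power 1.00. For effects of that size the cost is mainly a wider confidence interval.

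The equivalent sample sizes of 80 and 64 match the reported interval width at 50/50 but slightly overstate the power loss there: 80 patients without a period effect would have power 0.705, against 0.73 simulated. Finally, balanced blocks would make the imbalance shift close to nil. The plan does not state blocking, and loss before the second treatment could unbalance completers in any case. Balance also does nothing for the inflated standard error.

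**Conclusion.** The point holds. The planned tests are not wrong: with 1:1 allocation to sequence they keep their level and are unbiased on average. They do not use the sequence randomisation to remove a period effect. The loss is negligible if that effect is small relative to the SD of the differences (standard error up by about 3% at a quarter of an SD). It is material from half an SD: standard error up by about 12%, and power 0.71 instead of 0.80 where the design has 80% power. Where completed sequences are clearly unequal, the unadjusted estimate also moves by the period effect times the difference in sequence sizes divided by N.

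The SD, period effect and treatment effect are all assumed, because the documents give none of them; the ratios carry over to any SD if π is scaled with it. The change should be made because the possible gain is real and the cost is very small, not because the primary test is invalid.

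**What to change.** Replace the sentence in the Analytical Plan with:

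> Continuous outcomes will be analysed with a linear mixed model with fixed effects for treatment, period and sequence and a random subject effect, including all subjects with at least one evaluable study treatment. The treatment effect (alfentanil minus placebo) will be reported with a 95% confidence interval. Ordinal outcomes will be compared by a Wilcoxon rank-sum test of the within-subject period differences between the two sequences, using complete pairs. Paired t-tests and signed-rank tests will be reported as sensitivity analyses.

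This also removes the word that leaves the final analysis open. Name the degrees-of-freedom method for the mixed model; with complete pairs it should give the period-adjusted t-test used above, on 98 df. That complete-pair test is what was simulated, and it is an adequate simpler alternative. Including patients with only one study treatment is a small extra benefit, for continuous outcomes only.

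Cost: a change of wording and a few lines of code, with no extra data or patients, and one or two degrees of freedom. If there is no period effect, nothing is lost when sequences are equal. At 60/40 the adjusted standard error is (20/2) × √(1/60 + 1/40) = 2.04 against 2.00, about 1.5 power points (0.787 v 0.802).

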### **Human Subjects Protection/Confidentiality and Privacy**

Confidentiality will be protected by collecting only information needed to assess study outcomes, minimizing to the fullest extent possible the collection of any information that could directly identify subjects, and maintaining all study information in a secure manner. To help ensure subject privacy and confidentiality, only a unique study identifier will appear on the data collection form. Data access will be limited to study staff. Data and records will be kept locked and secured, with any computer data password protected. No reference to any individual participant will appear in reports, presentations, or publications that may arise from the study.

### **Data and Safety Monitoring**

The principal investigator will be responsible for the overall monitoring of the data and safety of study participants. In addition, to ensure the participants safety and integrity of the data, the Wake Forest Institutional Data Safety Monitoring Board (I-DSMB) will be used to monitor the trial.

### **Reporting of Unanticipated Problems, Adverse Events or Deviations**

Any unanticipated problems, serious and unexpected adverse events, deviations or protocol changes will be promptly reported by the principal investigator or designated member of the research team to the IRB or appropriate government agency if appropriate.

